Our retrospective clinical studies show that concurrent use of ACE inhibitors reduces the occurrence of radiation pneumonitis [and fibrosis], without lowering cancer-related survival. The safe mitigation of radiation injury has been identified as a priority by the National

Cancer Institute. We will address this critical problem. We hypothesize that the occurrence of radiation pneumonitis, fibrosis, or both in patients receiving radiation for lung cancer will be decreased by the ACE inhibitor enalapril, started after irradiation.

4. STUDY DESIGN. Provide a brief description of the design of the study (multicenter, double-blind, randomized, etc.) in narrative form. Do not provide details of specific procedures in this section (see Item 9 below). Include, as needed, a discussion of the appropriateness of research methods. Describe the statistical design and required sample size. Do not indicate "N/A" for this category.

This is a prospective, double-blinded, randomized, placebo-controlled trial, in a secondary-tertiary care setting. The ZVAMC and referring VAs in VISN 12 are the main centers; the Baltimore VAMC will be added. Subjects will join this trial voluntarily, based on their planned radiotherapy for lung cancer. We will enroll 200 subjects over the five years of this study. Statistical power analysis suggests the need for 200 subjects for the clinical endpoint, and ~ 100 subjects for the radiographic endpoint.

5. SUBJECT SELECTION AND EXCLUSION CRITERIA. Provide the specific criteria for including and excluding subjects in the study. Do not indicate "N/A" for this category.

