The study drug, enalapril or placebo, will be in addition to usual clinical care of subjects undergoing radiation therapy for lung cancer. Enalapril, or placebo, will be given orally, started within a day to up to 30 days of the beginning of the radiation treatments. They will be enrolled at the start of radiation therapy (RT), stratified for cancer stage, then randomized to enalapril or identical-appearing placebo. Randomization will be done by the Department of Biostatistics, Medical College of Wisconsin, using random number tables; the center pharmacies will be notified of the assignment to enalapril or placebo. There will be no stratification by age, gender, lung cancer histology, or use of chemotherapy since these do not have a consistent relation with the occurrence of RP. There is no stratification by center. Study drug is obtained from Expert Pharmacy Inc, with identical appearing enalapril and placebo tablets. It is held in the VA research pharmacy at Milwaukee, in a restricted access area under the aegis of the research pharmacist. It will be sent to patients at the Baltimore site upon their enrollment. The study drug dose will be

2.5 mg to start, and will be increased in increments of 2.5 mg to 10 mg per day, as tolerated. Clinical follow up of study subjects will be identical to that of subjects undergoing radiation therapy for lung cancer but who are not participating in this study, with the addition of four blood samples. One blood sample one week after starting the study will be to check for adverse effects of the study drug. Three more blood samples will be obtained for renin-angiotensin system (RAS) assays, done on three blood samples from each subject, at the start of the study, at 3 weeks after the start, and at the end of radiation therapy. Each of these four research-related blood samples will be approximately one teaspoon of blood obtained by venipuncture. Compliance is assessed by monitoring the requests for study drug refills. It will be verified at the end of the study by the elevation in plasma renin in subjects on enalapril compared to those on placebo. Study subjects will be monitored for adverse effects of study drug. The development, or not, of radiation pneumonitis and fibrosis will be assessed in the study subjects, as part of ongoing regular care, as are the periodic radiographic imaging and lung function testing. Quality of life will also be assessed.

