Cover page

Mitigation of radiation pneumonitis and fibrosis

ClinicalTrials.gov Identifier: NCT01754909

Most recent IRB approval Nov 13, 2017

Statistical methods plan

Power analysis for aim 1

For the RP endpoint, at an 11% rate of clinical RP, and an 80% mitigation effect, 97 subjects are needed per arm for type 1 error of 0.05 and a power of 0.80. The 11% and 80% figures are based on our retrospective studies. Only 49 are needed per arm for a baseline clinical RP rate of 20%. We plan for 200 subjects because there is variability in the rate of RP, and because we cannot be certain about the magnitude of efficacy of enalapril.

control	%difference	treatment	n/arm	total n
11%	50%	6%	306	612
11%	60%	4%	199	398
11%	70%	3%	136	272
11%	80%	2%	97	194
11%	90%	1%	70	140
20%	50%	10%	155	310
20%	60%	8%	101	202
20%	70%	6%	70	140
20%	80%	4%	49	98
20%	90%	2%	36	72

For a 50% radiographic rate of RP, and a halving of this by enalapril, 45 subjects are needed per arm.

50%	50%	25%	45	90
-----	-----	-----	----	----

50%	60%	20%	30	60
50%	70%	15%	21	42
50%	80%	10%	15	30
50%	90%	5%	11	22

For the radiographic fibrosis endpoint, at a 90% fibrosis rate, 29 subjects per arm would identify a 30% reduction in radiographic fibrosis at 6 or 12 months.

Endpoint and RAS analyses

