Dichotomous variables will be compared by chi-square, or Fisher's exact test, as indicated. Continuous variables will be compared by parametric or non-parametric statistics, as appropriate. Repeated measurements on the effects of enalapril and placebo on [RAS components] will be tested by a repeated measures ANOVA for continuous [RAS component] values and by a logistic type regression models [using GEE techniques for discrete [RAS component] values. In either case appropriate generalized linear models methods will be used to account for the association between repeated measurements over time on the testing procedure.] We will repeat the analysis using an appropriate regression analysis to account for possible patient factors which may influence outcome in addition to enalapril. We will also look at a model for RP and fibrosis using enalapril use and the RAS components as predictors as well as interactions between drug use and these predictors. Correlations will be made using Spearman's or Kendall correlation, as indicated. Dose modification factors (DMF) for the use of enalapril compared to placebo will not be tested since the expected radiation dose ranges will be too narrow. A more formal attempt to understand the mechanism of enalapril action on RP and fibrosis and determine if this is possibly derived through any one of the [RAS components] will use a structural equation modeling approach. This approach uses a matrix of regression coefficients from a series of regression models [of intermediate effects at the various time points to other intermediate effects at the same time point or to future intermediate or terminal effects. Using these coefficients and a postulated causal diagram which depicts which effects may be dependent on the patient history at a given time]. A final causal diagram which shows the relationship between drug, intermediate outcome and RP and or fibrosis [is constructed]. Path analysis techniques to construct the causal diagram can be constructed using the program DIGRAM (53). [This cited reference shows how this approach works by looking at causal factors for heart disease using data on behavioral factors measured at epochs in time.]

Survival analysis for aim 3

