Cancer-related survival and cancer recurrence will be compared for the enalapril and the placebo groups using Kaplan-Meier statistics. [We have calculated our ability to detect significant changes in cancer recurrence rates and in cancer survival, both for improvements in cancer-related outcomes and for adverse trends. We will be able to detect significant increases in recurrence rates or mortality. Our cohort of 162 subjects showed no difference in patient survival for those on ACE inhibitor compared to those not on ACE inhibitor. We do not

expect adverse changes in recurrence rates or patient survival. A mitigation benefit by enalapril could lead to an increase in patient survival, but less than a three month increase is not likely to be detected]

Recurrence rate change	Percent chance of detection
40 to 20 %	80%
40 to 60 %	81%

Cancer median survival change, months	Percent chance of detection
18 to 21	11%
18 to 12	60%

[There are potential pitfalls in the recurrence and survival analyses. These include the effects of interim sampling for the safety analyses, and adjustments for patient and disease characteristics as well as missing data.] The interim masked safety analyses will use the O'Brien correction to take into account the multiple analyses. In our analysis of survival, we will compare the recurrence-free survival rates between the treatment arms of the study in two ways. First we will examine the rates of death or recurrence using a Cox model. In this model we will adjust for patient/disease characteristics such as site of treatment, gender, age, stage of disease at randomization, and radiation dosage. We will also compare the disease free survival probabilities at two years using techniques that we have published (52). This method allows us to deal with the partial information available in patients who do not have a potential follow-up time of two years. This approach, which is a censored data version of logistic regression, will allow us to adjust the comparisons for patient, disease, and treatment factors. We picked two years here since the empirical evidence is that the disease-free survival curves tend to flatten out at around 20 months.

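### The two recurrence power figures for aim 3 (80% for 40 to 20%, 81% for 40 to 60%) do not follow from one sample size, sidedness and standard test; at 100 per arm the first should be about 88%

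*SAP*

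**What the plan says.** The SAP section on survival analysis for aim 3 states "We have calculated our ability to detect significant changes in cancer recurrence rates and in cancer survival" and adds that the calculation was done in both directions, benefit and harm. Its recurrence table has two rows: 40 to 20% with an 80% chance of detection, and 40 to 60% with 81%. The table carries no n, alpha, sidedness or test.

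The surrounding text supplies part of the basis:

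- **Sample size.** The SAP plans 200 subjects ("We plan for 200 subjects because there is variability in the rate of RP"), and the protocol's study design section agrees ("We will enroll 200 subjects over the five years of this study").
- **Allocation.** No ratio is given in words. In the aim 1 table the total is always twice the per-arm number, which implies 1:1 and so 100 per arm.
- **Alpha.** It appears only for clinical radiation pneumonitis: "97 subjects are needed per arm for type 1 error of 0.05 and a power of 0.80". Sidedness is not stated there either.
- **Test.** For binary outcomes: "Dichotomous variables will be compared by chi-square, or Fisher's exact test, as indicated". For recurrence: "Cancer-related survival and cancer recurrence will be compared for the enalapril and the placebo groups using Kaplan-Meier statistics", followed by an adjusted Cox model and a two-year comparison that handles incomplete follow-up.
- **Interim looks.** An O'Brien correction is named for the interim safety analyses, without boundaries or a final alpha.

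**The concern.** Both rows start from 40% and move 20 points. The binomial variance p(1−p) is 0.16 at 20% and 0.24 at 60%, so with the same n, alpha and test the fall is easier to detect than the rise. The table has them the other way round. The expected gap of several points in favour of the fall is too large to be rounding.

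Aim 3 is meant to confirm that enalapril does not worsen cancer outcomes, and this table is the SAP's numerical support for its ability to detect a change in recurrence. A reader who cannot rebuild the table from one basis cannot tell what sample size or sidedness it assumes. The question extends to aim 1: at 100 per arm the 81% fits a two-sided test, whereas the aim 1 sample sizes fit a one-sided one.

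**Working it through.** **Inputs.** From the SAP: recurrence 40% against 20% and 40% against 60%, and 200 subjects. Assumed: 1:1 allocation (100 per arm), two-sided 0.05, complete follow-up.

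**Formula.** Pooled comparison of two proportions: power = Φ[(|p1 − p2| − z·s0)/s1], where s0 = √(2p̄(1−p̄)/n), s1 = √((p1(1−p1) + p2(1−p2))/n) and z = 1.96.

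**Row 40 to 60%, n = 100.** p̄ = 0.50, s0 = 0.0707, s1 = √(0.48/100) = 0.0693. (0.20 − 0.1386)/0.0693 = 0.886, so power = 81.2%. The stated 81% reproduces.

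**Row 40 to 20%, n = 100.** p̄ = 0.30, s0 = 0.0648, s1 = √(0.40/100) = 0.0632. (0.20 − 0.1270)/0.0632 = 1.154, so power = 87.6%. The stated 80% does not reproduce.

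**Sample size implied by each row.** With the same formula, 80% for 40 to 20% needs 82 per arm, and 81% for 40 to 60% needs 100 per arm. At 82 per arm the pair is 80.4% / 73.0%.

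**Other methods at 100 per arm, alpha 0.05:**

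| Method | 40 to 20% | 40 to 60% |
|---|---|---|
| Stated in SAP | 80 | 81 |
| Pooled, two-sided | 87.6 | 81.2 |
| Unpooled, two-sided | 88.5 | 82.3 |
| Arcsine, two-sided | 87.8 | 81.3 |
| Exact power of chi-square, two-sided | 88.0 | 82.6 |
| Continuity-corrected, two-sided | 84.0 | 77.1 |
| Fisher's exact, two-sided | 84.4 | 78.7 |
| Log-rank, Schoenfeld, two-sided | 89.4 | 83.2 |
| Log-rank, Freedman, two-sided | 85.9 | 81.1 |
| Pooled, one-sided | 93.0 | 88.6 |

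**Search for a common n.** For each of these tests, one- and two-sided, no n from 50 to 120 per arm brings both figures within 2 points of those stated. For pooled and unpooled tests, with or without continuity correction, a search from 40 to 159 per arm still misses one figure by at least 3.6 points. Unequal splits (30 to 170 per arm, pooled two-sided) do not help.

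**Aim 1 sidedness.** n = [(z√(2p̄(1−p̄)) + 0.842√(p1(1−p1) + p2(1−p2)))/(p1 − p2)]². For 11% with 80% mitigation, p2 = 0.022, p̄ = 0.066, and the two roots are 0.3511 and 0.3456.

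- One-sided (z = 1.645): ((0.5775 + 0.2909)/0.088)² = 97.4, so 98 per arm; the SAP states 97.
- Two-sided (z = 1.96): ((0.6882 + 0.2909)/0.088)² = 123.8, so 124 per arm.
- Two-sided power at 100 per arm: (0.088 − 0.0688)/0.0346 = 0.555, so 71%.

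All 16 scenarios in the aim 1 section lie 1 to 3 subjects per arm below the one-sided result. For example, 20% halved gives 157 one-sided and 199 two-sided, against 155 stated.

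**The case against.** Three points can be made for the table.

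First, a reader might infer that no sample size at all can give 80% and 81%. That goes too far. Both figures fit within 2 points at about 78 to 83 per arm if benefit is tested two-sided and harm one-sided (pooled), or at about 92 to 99 per arm if the 40% control variance is used in both arms (two-sided). The documents describe neither construction, so they do not rescue the table, but they limit the claim to one common sidedness and a standard test.

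Second, a reader might take 88% as the power of the planned aim 3 analysis. The documents do not support that. They state no two-sided alpha for this table, and they plan Kaplan-Meier and Cox methods, in which the benefit scenario also has fewer events. That narrows the gap to about 4 to 5 points (Freedman: 85.9% and 81.1%) but keeps its direction. An interim correction lowers both rows: with an assumed final alpha of 0.043 the pooled pair is 86.2% / 79.4%.

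Censoring and competing death lower them further. As an illustration, take the rates as 24-month figures with exponential hazards, median death at 18 months, 60 months of accrual and 0 to 12 months of further follow-up. The 40-to-20% hazard ratio is ln 0.8/ln 0.6 = 0.437, with about 39 to 47 recurrences. Freedman's power, Φ[√E·(1 − HR)/(1 + HR) − 1.96], is then about 69 to 76%. These inputs are assumptions; the documents give none of them for this table.

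Third, the row that fails is the benefit row, and it understates power. A reader might infer that the aim 3 claim about detecting harm falls with it. It does not: on the simple basis the harm row reproduces. This limits the importance of the point but does not remove the inconsistency.

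**Conclusion.** The point stands as a minor error in reporting. Under one n, one sidedness and a standard test, 80% and 81% do not go together. At 100 per arm, two-sided 0.05, the 40-to-20% row is understated by about 8 points (87.6% against 80%; 84 to 89% across two-sided tests), while the 40-to-60% row is right. This rests on 1:1 allocation, an assumed two-sided 0.05, crude proportions or simple event counts, and full follow-up with no interim adjustment. No planned sample size depends on the recurrence table.

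The difference in sidedness between the two power sections is also real, and it has more effect on the figures. The aim 1 sizes are one-sided, and on that convention the recurrence pair at 100 per arm would be 93% and 89%, matching neither printed figure. A reader might conclude that the trial must enrol 124 per arm. That does not follow: the documents never say which sidedness the aim 1 test will have. If it is two-sided, what needs restating is the power available at 200 subjects.

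**What to change.** 1. Beside the recurrence table, state n per arm, alpha, sidedness, test and follow-up assumption, and recompute both rows on that single basis. For a pooled two-sided 0.05 comparison at 100 per arm with full follow-up, the rows read about 88% and 81%. If censoring, competing death or the interim correction is allowed for, give the lower figures and the assumptions behind them. If an unusual construction was used, describe it.
2. In the aim 1 power section, state that the sample sizes assume a one-sided 0.05. If a two-sided test is intended, as the 81% implies, restate the aim 1 figures at the planned 200 subjects rather than enrolling more. For 11% with 80% mitigation, 80% power would need about 124 per arm, and 100 per arm gives about 71%.

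The first change costs two numbers and a sentence. The second costs one sentence if one-sided is kept, or a recalculated aim 1 table if not. Neither changes enrolment or study conduct.

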Cover page

Title: Mitigation of radiation pneumonitis and fibrosis

ClinicalTrials.gov Identifier: NCT01754909

Most recent IRB approval Nov 13, 2017

Protocol for “Mitigation of radiation pneumonitis and fibrosis”

Cohen VA 1531-01, CLIN-004-12S

Original from Oct 31, 2012 Registration packet, incorporating amendments through July 2015

Objective

This project will test the effect of enalapril, an angiotensin-converting-enzyme inhibitor, to mitigate radiation pneumonitis and fibrosis in veterans undergoing radiation therapy for lung cancer and other cancers in the chest. It is based on the hypothesis that human normal tissue radiation injury can be safely and effectively mitigated, and on our extensive studies of radiomitigation in experimental animals. Lung cancer is more common in veterans than in the general population; this project is highly relevant to the medical care of veterans.

Research design and methodology

Enalapril or placebo will commence after the start of irradiation in veterans undergoing radiation therapy for lung cancer and other cancers in the chest, and their effects on radiation pneumonitis and fibrosis will be compared as the primary outcome measure. Enalapril will be used rather than captopril, because enalapril is given in single daily doses. This is a prospective, double-blinded, randomized, placebo-controlled trial, in a secondary-tertiary care setting. Subjects will join this trial voluntarily, based on their planned radiotherapy for lung cancer, and it is planned to enroll 200 subjects over the five years of this study. The intervention of this study is the use of enalapril or placebo, which will be maintained for the lifetime of the study subject.

2. To test the mechanism of mitigation of radiation lung injury by enalapril.
 - a. Angiotensinogen, plasma renin activity, and angiotensin II will be measured as renin-angiotensin system markers in all subjects.
 - b. The effect of enalapril on each marker will be assessed, as compared to placebo.
3. To confirm that enalapril in this use does not adversely affect cancer treatment outcomes.
 - a. Cancer recurrence and death from cancer will be compared for the enalapril and placebo groups.

These studies will be done in men and women undergoing radiation therapy for lung cancer and other cancers in the chest. Enalapril, or identical-appearing placebo, will be started within a day

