- f. Studies will be stopped when there is a greater than expected rate of morbidity or mortality or when the experimental arm of a head to head comparison study is shown to be better or worse statistically than the standard care arm, taking into account any multiple comparison statistical issues.

13. **COMPENSATION OF SUBJECTS.** Provide the terms of the subject participation agreement and the amount of payment. Substantiate that proposed payments are reasonable

and commensurate with expected contributions of the subject and that they do not constitute (or appear to constitute) undue pressure on the subject to volunteer for the research study. Describe any non-VA compensation for injured research subjects.

No compensation will be provided

14. **PRIVACY.** Provide provisions to protect the privacy interests of subjects. Indicate that all research personnel will respect the dignity, cultural, psychosocial, spiritual and personal values, beliefs, preferences, and personal privacy of research subjects as outlined in Medical Center Memorandum 00-102. In every subject encounter, members of the research team must be sensitive to the subject's gender, cultural, psychosocial, spiritual and personal values, beliefs and preferences, and how the subject may interact with the procedure to be performed, especially if the procedure involves intimate physical aspects. Personal privacy includes pulling cubicle curtains around a bed, closing the room door while providing care or interviewing a subject, providing auditory privacy, knocking on a room door before entering, covering the subject appropriately both in privacy and in public areas, etc.

All research personnel will respect the dignity, cultural, psychosocial, spiritual and personal values, beliefs, preferences, and personal privacy of research subjects as outlined in Medical Center Memorandum 00-102. In every subject encounter, members of the research team will be sensitive to the subject's gender, cultural, psychosocial, spiritual and personal values, beliefs and preferences, and how the subject may interact with the procedure to be performed. Personal privacy includes pulling cubicle curtains around a bed, closing the room door while providing care or interviewing a subject, providing auditory privacy, knocking on a room door before entering, covering the subject appropriately both in privacy and in public areas.

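### Aim 3 sets out to confirm no harm to cancer outcomes, but the plan gives no basis for that conclusion, and its sentence on detecting increased mortality is too strong beside its own 60% figure

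*SAP*

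**What the plan says.** The protocol's aim 3 (numbered aims under Research design and methodology) reads "To confirm that enalapril in this use does not adversely affect cancer treatment outcomes". Its sub-aim 3a adds "Cancer recurrence and death from cancer will be compared for the enalapril and placebo groups".

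The SAP section Survival analysis for aim 3 plans three things:
- "Cancer-related survival and cancer recurrence will be compared for the enalapril and the placebo groups using Kaplan-Meier statistics".
- For recurrence-free survival, "we will compare the recurrence-free survival rates between the treatment arms of the study in two ways". The first way is a Cox model for death or recurrence, adjusted for patient and disease factors.
- The second way is an adjusted comparison of disease-free survival at two years.

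On sensitivity, the same section says "We have calculated our ability to detect significant changes in cancer recurrence rates and in cancer survival", and then "We will be able to detect significant increases in recurrence rates or mortality". The tables beneath give these chances of detection:
- Recurrence: 80% for 40 to 20%, and 81% for 40 to 60%.
- Median survival: 11% for 18 to 21 months, and 60% for 18 to 12 months.

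The section cautions that a survival gain of under three months would probably go unnoticed. It gives no matching caution for harm. It does not state the number of subjects, follow-up, loss to follow-up, sidedness or method behind the tables.

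**The concern.** A comparison that finds no significant difference is not evidence that there is none, and least of all when it has moderate power. Aim 3 promises a no-harm conclusion. The plan does not say whether that conclusion would rest on a p-value, a confidence limit or a margin, so a non-significant result could be reported as confirmation.

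The unqualified detection sentence makes that reading easier, because it suggests that a real increase in mortality would have shown itself. At stake is any later statement that enalapril during chest radiotherapy is safe for cancer control and survival. That statement could be made when the data still allow a material increase in deaths.

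**Working it through.** **Inputs.** From the documents: 200 subjects over five years (Protocol, item 4), and the four table rows (SAP, Survival analysis for aim 3). The error rate comes from aim 1 (SAP, Power analysis for aim 1: "97 subjects are needed per arm for type 1 error of 0.05 and a power of 0.80") and is assumed to carry over. Also assumed: 1:1 allocation (100 per arm), two-sided testing, exponential survival, control median 18 months. Follow-up is not stated. The range used runs from 18 months fixed to 60 months of uniform accrual plus 24 months. Yearly loss is assumed to be 0, 10 or 20%; censoring at a non-cancer death acts in the same way.

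**Step 1. The SAP's 60%.** 18 to 12 months is HR = 18/12 = 1.5. Log-rank power = Φ(|ln HR|·√D/2 − 1.96), with D the total deaths.
- Solving for 60% gives D ≈ 119.
- With 18 months fixed and no loss, deaths are 100×(1 − 0.5) = 50 on control and 100×(1 − 0.5^1.5) = 64.6 on enalapril, so D = 114.6. Power = Φ(0.4055×10.70/2 − 1.96) = Φ(0.21) = 58%.
- With 20 months fixed, power is 61%, and 12% for the 18 to 21 row.
- With 60-month accrual, no further follow-up and 10% yearly loss, power is 60% and 12%.

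So the 60% is reproducible, but several settings fit and the table does not reveal which was used.

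**Step 2. Range of power, and what a null-looking result would exclude.** Let D0 be the deaths expected with no drug effect. For an observed HR of 1.0, the upper 95% limit is exp(1.96×2/√D0). For D0 = 100 this is exp(0.392) = 1.48.

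| Follow-up | Yearly loss | Power 18 to 12 | Power 18 to 15 | D0 | Upper limit |
|---|---|---|---|---|---|
| 18 months fixed | 0% | 58% | 15% | 100 | 1.48 |
| 60 + 24 months | 0% | 77% | 22% | 169 | 1.35 |
| 18 months fixed | 10% | 56% | 15% | 93 | 1.50 |
| 60 + 24 months | 10% | 71% | 20% | 146 | 1.38 |
| 18 months fixed | 20% | 53% | 14% | 87 | 1.52 |
| 60 + 24 months | 20% | 66% | 18% | 125 | 1.42 |

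Simulated log-rank tests (6,000 trials per setting) agree for 18 to 12 months, for example 59% and 77% without loss and 53% and 65% with 20% loss. A one-sided 0.05 test at 119 deaths would have 71.5%.

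**Step 3. Recurrence rows.** Two-proportion test with pooled variance, 100 per arm, two-sided:
- 40 to 60%: (0.20 − 1.96×√(2×0.5×0.5/100)) / √((0.24 + 0.24)/100) = 0.886, power 81%, as stated.
- 40 to 20%: (0.20 − 1.96×√(2×0.3×0.7/100)) / √((0.24 + 0.16)/100) = 1.154, power about 88%, against the stated 80%.
- The stated 80% fits about 82 per arm, at which 40 to 60% would have 73%. By this method the two rows do not share one N.
- Smaller harms at 100 per arm: 40 to 55% has 57%, and 40 to 50% has 29%.

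**Step 4. If a margin were used.** With no drug effect, the chance that the upper limit falls below an illustrative HR of 1.3 is Φ(ln 1.3·√D0/2 − 1.96). This is 26 to 40% without loss and 23 to 35% with 10 to 20% yearly loss.

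**The case against.** Five points can fairly be made for the plan.

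- The 60% is printed directly below the sentence it qualifies, in a table of detection chances. That stands. A reader might infer that low power was hidden, or that the trial misses a power target for aim 3. Neither is supported: the figure is open, and the SAP sets no power standard for this aim.
- The SAP nowhere says that a non-significant p-value will count as confirmation, and a Cox model ordinarily yields a hazard ratio with an interval. That also stands. The point is that the plan leaves this reading open and does not say what would support the word *confirm*.
- Harm is monitored. Safety data go to the monitoring committee at 50, 100, 150 and 200 subjects, interim safety analyses use an O'Brien correction, and "Studies will be stopped when there is a greater than expected rate of morbidity or mortality" is the stopping statement (Protocol, item 12f). These may catch some harm. They carry no numeric limit, and not stopping is not evidence of no harm.
- This is the third aim of a phase 2 trial sized on aim 1. A reader might infer that a non-inferiority margin is obligatory or that the trial is too small. Neither follows. The primary aim is untouched, and rewording the aim is enough.
- The ranges in the working rest on assumptions. That stands; only the 60% is the SAP's own. The ranges also ignore any final-look penalty. If the O'Brien correction applied to survival, with a critical value of about 2.02, power would fall by some 2 to 3 points (58% to 56% at 18 months fixed).

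**Conclusion.** The point holds on both parts. First, aim 3 asks for a conclusion that the stated analyses cannot support, because they compare the arms and no basis for concluding no harm is given. Second, the detection sentence is too strong for mortality beside the disclosed 60%. For recurrence it has support only for a rise as large as 40 to 60%.

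No follow-up and loss setting in the working's table reaches 80% power for 18 to 12 months (53 to 77%), and 18 to 15 months has 14 to 22%. Even a perfectly null estimate would not exclude a hazard of death about 35% higher in the most favourable setting, or 52% higher in the least. These ranges assume 100 per arm, two-sided 0.05, exponential survival with an 18-month control median, and the follow-up and loss given in the working.

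This should be fixed, but it does not threaten the primary result. The recurrence-row mismatch (about 88% computed against 80% stated) is in the favourable direction. It does not create the problem, but the rows need checking before any figure is restated.

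**What to change.** (a) In the protocol, reword aim 3 to *estimate and bound the effect of enalapril on cancer outcomes*. In the SAP, report the treatment hazard ratio with its 95% confidence interval from the planned Cox model for death or recurrence, and likewise for the two aim 3a outcomes, cancer recurrence and death from cancer. State that a non-significant difference will not be taken as confirmation of no harm. A margin rule is optional. If the sponsor wants one, it should be justified in advance, with *inconclusive* as the result when it is not met.

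(b) Limit the detection sentence to the tabulated effects: 60% for median survival falling from 18 to 12 months, less for smaller harms, and the recurrence figure only for a rise from 40 to 60%. Recheck both recurrence rows first, and state the N, method, follow-up, loss to follow-up and sidedness behind all four rows.

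**Cost.** The change is wording in two documents plus interval reporting, with hazard ratios added for the two aim 3a outcomes. Sample size, data collection and the primary aim do not change. The downside is that the stated ability to rule out harm becomes less favourable. A tight margin would often end as inconclusive (an illustrative 1.3 would be met only 23 to 40% of the time with no drug effect), which is why rewording the aim is the more practical route.
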